## 1.2 SCHEMATIC OF STUDY DESIGN

An overview of the study design is provided in [Figure 1](#).

**Figure 1 Overview of Study Design**

[figure not shown]
### A. PART 1 - 52-week double-blind placebo controlled (main study)

D= Day; IMC = Internal Monitoring Committee; N = number of participants; PK = pharmacokinetics; qEEG = quantitative EEG; SOC = Scientific Oversight Committee.

\* The follow-up period will not be completed for participants entering Part 2.

### B. PART 2 - optional open-label extension (OLE) of 2 years

## 1.3 SCHEDULE OF ACTIVITIES

The schedule of activities (SoA) for Part 1 is provided in [Table 1](#) (overview of Part 1) and [Table 2](#) (Part 1 detailed table). The SoA for Part 2 is provided in [Table 3](#) (Part 2 - optional open-label extension [OLE]) and [Table 4](#) (Part 2 - optional OLE - detailed table).

**Table 1 Schedule of Activities for Part 1 – Overview**

Period	Screening a	Baseline b	Treatment Period/Visit							Final Visit	Follow-up c, q	Early Termination c
Day	Day -35 to Day -2	Day -7 to Day -1	Day 1	Day 2	Day 14	Day 28 d	Day 92 c	Day 183 b	Day 274 c	Day 365 b	Day 395	Anytime
Weeks (approximate)	Week -5 to Week -1	Week -1	Week 1	Week 1	Week 2	Week 4	Week 14	Week 26	Week 40	Week 52	Week 56	
Visit window					± 5 days	± 5 days	± 7 days	± 7 days	± 7 days	± 7 days	± 10 days	
Assessments												
Informed consent	x									x t		
Inclusion/Exclusion criteria	x	x										
Caregiver expectation guidance u	x	x						x		x		
Randomization		x										
Demography	x											
Medical history	x											
Physical examination e	x	x						x		x		
Assessment of hypotonia		x		x	x			x		x		
Vital signs	x	x	x	x	x		x	x	x	x q	x	x
Genetic test : CMA r	x											
Genetic test : MS-MLPA r	x											
Genetic test: FISH r					x							
Pregnancy test f	x	x					x	x	x	x q	x	x
Urinalysis	x	x			x		x	x	x	x q	x	x
Hematology	x	x			x		x	x	x	x q	x	x
Clinical chemistry	x	x			x		x	x	x	x q	x	x
Coagulation	x											
Viral serology	x											
Thyroid hormones	x									x q		
RBR whole blood sample (optional)		x										
Tanner staging g		x								x		
12-lead ECG (triplicate)	x	x	x	x	x			x		x q		
Seizure status h		x				x	x	x	x	x	x	x
EEG monitoring i		x	x	x	x			x		x q		
Study drug administration j			◀							▶		
PK sample k			x	x	x		x	x	x	x q		x
Dup15q CGI-S h	x	x				x	x	x	x	x	x	x
Dup15q CGI-C h						x	x	x	x	x	x	x

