**Table 1 Schedule of Activities for Part 1 – Overview (cont.)**

ABC-2-C = Aberrant Behavior Checklist - Second Edition – Community Version; ADOS = Autism Diagnostic Observational Schedule, second edition; BID = twice a day; CMA = *chromosomal microarray*; CSHQ = Children's Sleep Habit Questionnaire; Dup15q CaGI-C = Dup15q syndrome Caregiver Global Impression of Change scale; Dup15q CaGI-S = Dup15q syndrome Caregiver Global Impression of Severity scale; Dup15q CGI-C = Dup15q syndrome *Clinician Global Impression of Change scale*; Dup15q CGI-S = Dup15q syndrome *Clinician Global Impression of Severity scale*; FISH = *fluorescence in situ hybridization*; MSEL = Mullen Scales of Early Learning; MS-MLPA = *methylation specific-multiplex ligation-dependent probe amplification*; ORCA = Observer-Reported Communication Ability; PedsQL-FIM = Pediatric Quality of Life Inventory™ Family Impact Module; PK = pharmacokinetics; qEEG = quantitative EEG; RBR = Research biosample repository; RBS-R = Repetitive Behavior Scale-Revised; TID = three times a day; Vineland-3 = Vineland Adaptive Behavior Scales–Third Edition.

- a Screening period starts once first screening assessment is performed; informed consent can be signed earlier. *All screening assessments required to confirm participant's eligibility for study participation need to be completed with results available before the Baseline visit. The Baseline visit can be done anytime between Day -7 and Day -1.*
- b Visit can be split over two consecutive days if needed.
- c Visit *can be* done remotely if local regulations allow for it and if home nursing service is available in the country/region.
- d Telephone call only.
- e Height and head circumference do not need to be recorded at Baseline.
- f Urine pregnancy test for female participants of childbearing potential. If the urine pregnancy test is positive, it must be confirmed by a blood pregnancy test.
- g For participants aged 9 years and above at the time of signing the Informed Consent Form. Once a participant reaches Stage 5, Tanner staging no longer needs to be performed.
- h Performed by the clinician either at the clinic visit or via telephone/video call at the remote/telephone call visits.
- i See the detailed schedule in [Table 2](#) for length of EEG and timing of qEEG timepoints.
- j Study treatment administration is BID on Day 1 and TID from Day 2 onward.
- k See detailed schedule in [Table 2](#) for exact PK timings.

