- either not expected based on previous clinical experience in adolescents and children with Down syndrome and in CIAS (i.e., heart rate and blood pressure changes, lipids and cholesterol, effect on body weight) or
- deemed not clinically significant for the pediatric population with Dup15q syndrome (i.e., modest increase in serum creatinine related to the inhibition of its tubular secretion by basmisanil) included in this study.

For a complete summary, refer to the [Basmisanil Investigator's Brochure](#).

Because of the effect of CYP3A4 inhibitors on the PK of basmisanil, there is a potential risk of QTc prolongation. However, because the use of strong CYP3A4 inhibitors is prohibited in this study (see Section 6.5.2), this risk of QTc prolongation is considered low for this study.

PK DDIs through inhibition of P-gp efflux are mitigated by prohibiting DOACs and advising that other P-gp substrates should be used with caution (see Section 2.2.3.2.2, Section 6.5.2, and Section 6.5.3).

PD DDIs through interaction with GABAA receptors are mitigated by advising that drugs acting through GABAA receptors may require a higher dose to reach the desired effect when participants are taking basmisanil (see the [Basmisanil Investigator's Brochure](#), Section 6.5.3, and Table 12).

See the [Basmisanil Investigator's Brochure](#) for more details.

There is currently no known immunotoxic effect or increased risk of infection under basmisanil treatment. However, in the setting of a pandemic or epidemic, screening for active infections prior to and during study participation should be considered according to local/institutional guidelines, and basmisanil treatment should not be administered to participants with active, confirmed, or suspected, COVID-19 due to potential severity of this infection. In case of closing of the hospital facilities due to COVID-19, investigators should follow up with the participants as needed and at least follow the normal dosing schedule (i.e., call the participant for AE recording and ask for safety laboratory tests in local laboratories or other investigations (e.g., ECG) as a substitute for investigations scheduled at investigational facility if required).

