**Table 5 Objectives and Endpoints for Part 1 (cont.)**

Objectives	Endpoints
Secondary (cont.)	
Safety (cont.)	

 
To evaluate the tolerability and safety of 52 weeks of treatment with basmisanil
 
	
 
Abnormal changes in EEG recordings compared to baseline with a focus on treatment-emergent epileptiform abnormalities
 
Systolic and diastolic blood pressure and heart rate measurements
 
Suicidality as assessed through questions from selected items adapted from the C-CASA in participants aged 6 years and above
 
Height, weight, head circumference
 
Tanner staging over time (in participants aged 9 years and above)
 

PK	

 
To characterize the PK of basmisanil and its metabolite M1 [REDACTED]
 
To evaluate potential relationships between selected covariates and exposure to basmisanil
 
	
 
Plasma concentration of basmisanil and its major metabolite M1 at specified timepoints.
 
PK parameters for basmisanil: <math>AUC_{\text{tau,ss}}</math>, <math>C_{\text{max,ss}}</math>, <math>C_{\text{trough,ss}}</math>, <math>CL/F</math>, <math>Vd/F</math>
 
Plasma concentration ratio of M1 to basmisanil at trough
 
PK parameters for M1: <math>C_{\text{max,ss}}</math>, <math>C_{\text{trough,ss}}</math>
 
Other PK parameters as appropriate
 

PD	

 
To evaluate the effects of basmisanil treatment on the characteristic Dup15q EEG phenotype acutely and at steady state
 
	
 
qEEG beta-band power
 

$AUC_{\text{tau,ss}}$  = area under the concentration–time curve during one dosing interval at steady state;  
 C-CASA = Columbia Classification Algorithm for Suicide;  $CL/F$  = apparent clearance;  $C_{\text{max,ss}}$  = maximum concentration at steady state;  $C_{\text{trough,ss}}$  = trough plasma concentration at steady state;  
 PD = pharmacodynamics; PK = pharmacokinetics; qEEG = quantitative EEG;  $Vd/F$  = apparent volume of distribution.

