### **7.1 DISCONTINUATION OF STUDY TREATMENT**

For data to be collected at the time of treatment discontinuation and follow-up and for any further evaluations that need to be completed see the SoA (Section 1.3).

Reasons for discontinuation of study treatment may include, but are not limited to, the following:

- Any medical condition that the Investigator or Sponsor determines may jeopardize the participant's safety if he or she continues study treatment.
- Investigator or Sponsor determination that treatment discontinuation is in the best interest of the participant.
- Participant suicidal behavior or active suicidal ideation with specific plan and intent.

- An event that meets the stopping criteria (see Section 4.1.3).
- Pregnancy.
- Specific AEs if discontinuation of study treatment is required to manage the event (see Section 8.3.8).
- Symptomatic participants with moderate or severe COVID-19 infection (as per WHO guidelines) with signs of pneumonia or hypoxia.

Every effort should be made to obtain information on participants who discontinue study treatment but have not withdrawn consent. Participants who discontinue study treatment prematurely (*Part 1 or Part 2*) will be asked to return to the clinic for a study early termination visit (see Section 8.10.3) and *will be asked to complete the follow-up visit* (see Section 8.10.4), unless the participant withdrew consent. The primary reason for premature study treatment discontinuation should be documented on the appropriate eCRF.

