### **8.2.2 Physical Examinations**

A complete physical examination should include an evaluation of the head, eyes, ears, nose, throat, neck and lymph nodes, and the cardiovascular, dermatological, musculoskeletal, respiratory, gastrointestinal, genitourinary, and neurological systems.

Any abnormality identified at baseline should be recorded on the General Medical History and Baseline Conditions eCRF.

Weight, height and head circumference: Body weight (using calibrated scales) will be measured to the nearest 100 g at the timepoints specified in the SoA (Section 1.3). Head circumference will be measured in children below the age of 5 years to the nearest 0.1 cm using a flexible, non-stretchable tape.

*Abnormal* changes from baseline should be recorded in participant's notes. New or worsened clinically significant abnormalities should be recorded as AEs on the Adverse Event eCRF.

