## **8.2.5        Vital Signs**

Blood pressure, pulse rate, respiratory rate, and body temperature (oral or tympanic) will be recorded at the timepoints specified in the SoA (Section 1.3). Blood pressure, pulse rate, and respiratory rate should be obtained in a quiet room at a comfortable temperature, with the participant's arm unconstrained by clothing or other material. The participant should be asked to remove all clothing that covers the location of cuff placement. All measurements will be obtained from the same arm and, with the appropriate cuff size, using a well-calibrated automatic instrument with a digital readout, throughout the study (the “ideal” cuff should have a bladder length that is 80% and a width that is at least 40% of arm circumference [a length-to-width ratio of 2:1]). The individual should be comfortably in a semi-supine/supine position, with the legs uncrossed.

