### **8.10.3 Assessments at Early Termination Visit**

Participants who discontinue from the study early will be asked to complete early termination assessments as per the SoA (Section 1.3) as soon as possible after the final dose of study treatment.

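### Part 1 schedules no weight, height or physical examination at Early Termination, so a child who stops before Day 183 has no planned post-baseline growth value

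*Combined protocol and SAP*

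**What the plan says.** Table 1 (Section 1.3) has twelve visit columns for Part 1. The "Physical examination" row is marked in four: Screening, Baseline, Day 183 and Day 365. Early Termination and Follow-up (Day 395) are blank. Footnote e on that row states: "Height and head circumference do not need to be recorded at Baseline".

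Section 8.2.2, Physical Examinations, covers weight, height and head circumference. It leaves the timing of weight to the schedule: "Body weight (using calibrated scales) will be measured to the nearest 100 g at the timepoints specified in the SoA". Head circumference is measured only in children under 5 years. Table 1 has no separate row for weight.

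Section 8.2.5 defines vital signs without weight: "Blood pressure, pulse rate, respiratory rate, and body temperature (oral or tympanic) will be recorded at the timepoints specified in the SoA".

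Under Section 7.1, a participant who stops treatment prematurely "will be asked to return to the clinic for a study early termination visit" and is then asked to complete the follow-up visit. Section 8.10.3 adds no list of its own: "Participants who discontinue from the study early will be asked to complete early termination assessments as per the SoA".

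Table 5 lists "Height, weight, head circumference" among the Part 1 secondary safety endpoints. Section 9.3.3 plans to describe these data in summaries and/or listings. For Part 2, Table 3 marks the physical examination at Day 548, Day 730, Day 1095, Follow-up and Early Termination.

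**The concern.** Growth is a stated safety endpoint of the placebo-controlled year, but the schedule collects it after baseline only at the two clinic visits attended by children still in the study at months 6 and 12. A child who leaves earlier passes through an Early Termination visit that takes vital signs, blood and urine but not weight.

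What is at stake is completeness, not the primary endpoint. The growth summaries would contain no post-baseline value for anyone who stops in the first half of the year, and a value of increasing age for those who stop in the second half. Whether the missing children differ from the others could not be checked, because nothing was measured when they left.

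Part 1 is also the only part in which growth can be compared with placebo. Part 2 has no control arm and its safety objective is exploratory, yet it has the fuller closing assessment.

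**Working it through.** No sample-size, power or alpha figure is involved. The check is a reading of the schedule and a simple scale calculation.

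**1. Where the examination is marked**

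| Schedule | Columns marked | Early Termination | Follow-up |
|---|---|---|---|
| Table 1 (Part 1), 12 columns | Screening, Baseline, Day 183, Day 365 (4 of 12) | blank | blank |
| Table 3 (Part 2), 7 columns | Day 548, Day 730, Day 1095, Follow-up, Early Termination (5 of 7) | marked | marked |

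The first on-treatment examination in Part 1 is at 183 / 7 = 26.1 weeks, with a window of ± 7 days. That is 183 / 365 = 0.50 of the treatment year.

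**2. Whether another row supplies growth data**

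- Vital signs are marked at Early Termination and Follow-up, but their definition in Section 8.2.5 does not include weight.
- Clinical chemistry is marked at both visits and carries no growth measure.
- Hypotonia is assessed at Baseline, Day 2, Day 14, Day 183 and Day 365. Section 8.1.5.9 limits it to head control and truncal stability.
- Footnote e ties height and head circumference to the examination row. Placing weight there is an inference from Section 8.2.2, which handles all three measures together.
- Only the footnotes of Table 2 are in the public text. None of them mentions weight, but an entry in its grid cannot be ruled out.

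**3. What a child who stops early contributes**

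| Time of stopping | Scheduled post-baseline examinations and growth measurements | Age of last value at stopping |
|---|---|---|
| Before Day 183 | 0 | none exists |
| Between Day 183 and Day 365 | 1 (Day 183) | up to 365 − 183 = 182 days, about 6 months |

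The pre-treatment values exist: weight at Baseline, and height and head circumference at Screening, since footnote e waives them at Baseline.

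**4. Scale**

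Section 9.1 plans about 90 randomized participants with about 10% not evaluable for efficacy. Its own figure reproduces: 90 × (1 − 0.10) = 81 evaluable, so 90 × 0.10 = 9 are not. The documents give no rate or timing of early stopping. If one assumes that early stopping equals this allowance, 9 children stop early, split 6 and 3 at 2:1 randomization if it is equally frequent in both arms. The number stopping before Day 183 then lies anywhere from 0 to 9.

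**The case against.** The strongest reply is that the blank is deliberate. Footnote c and Section 8 (Remote visits) allow the Part 1 Day 92, Day 274, Early Termination and Follow-up visits to be done at home by a mobile nurse. All four lack the physical examination, the ECG and the EEG. In Table 3 the Early Termination and Follow-up visits carry no remote option, and ECG and thyroid tests appear there as well. A reader might infer from the difference between the two tables that a mark was simply forgotten; the documents do not support that, because the pattern follows the mode of visit. This part of the reply stands. It explains why a full examination is absent, but not why weight is, since a nurse who takes vital signs and blood can also weigh a child.

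Three other inferences go too far.

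- **A weight signal.** Section 2.3.1.2 does name "heart rate and blood pressure changes, lipids and cholesterol, effect on body weight" among other potential risks, but as ones not expected on earlier clinical experience. The case for measuring weight rests on the Part 1 endpoint list, not on a suspected effect.
- **No closing assessment at all.** Vital signs, laboratory tests, seizure status, clinician global ratings and adverse events are collected at Early Termination. Section 8.3.3.1 requires adverse events to be followed, and Appendix 2 calls for further evaluations as medically indicated. What is missing is the scheduled general examination and the growth measurements.
- **A biased growth comparison.** A reader might assume that early stoppers leave mostly because of adverse events, so that the summaries describe those who tolerate treatment. The documents give no reasons or rates for stopping, and growth is to be described, not formally tested. Selection is possible but cannot be shown or sized.

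It is also fair to say that height or head circumference after a few weeks on treatment carries little information, and that a repeat examination at Follow-up would add little for children already examined at Day 365.

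**Conclusion.** The gap holds on the public text. Part 1 has two scheduled post-baseline physical examinations, at Day 183 and Day 365, and no readable part of the protocol schedules weight or height at any other post-baseline visit. A child who stops before Day 183 has none of these values; a child who stops later has the Day 183 values only.

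The number of children is unknown. The range of 0 to 9 of 90 rests on treating the 10% efficacy-evaluability allowance as a rate of early stopping, which the protocol does not do; a reader should not take 9 as the expected loss. The conclusion also assumes that weight follows the examination row and that the grid of Table 2 contains no weight entry at Early Termination.

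The primary analysis is unaffected. This is a modest, avoidable hole in a named secondary safety endpoint, at a visit that already takes place, and it is worth closing.

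**What to change.** In the Early Termination column of Table 1, add weight and height, with head circumference for children under 5 years, and add the physical examination when the visit is held in clinic. When the visit is remote, the mobile nurse records at least weight, on a calibrated scale that meets the precision set in Section 8.2.2. If the grid of Table 2 already schedules weight at that visit, a cross-reference is enough for that item.

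In the analysis plan for Section 9.3.3, include this value in the descriptive growth summaries as a separate early-termination value, with the days since last dose. The visit takes place after the final dose, so the value should not be labelled as on-treatment.

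No addition at Follow-up is needed, and no full examination at a remote visit.

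Cost: a short amendment to Table 1, a few minutes at an existing visit, and a calibrated scale for home visits. Children seen remotely would still have no full closing examination.

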#### **2.3.1.2 Potential Risks for Basmisanil**

The potential for a pro-convulsive risk was evoked with the results of the pentylenetetrazole (PTZ) test, a potent pro-convulsant, in which sub-threshold doses of PTZ given with basmisanil were associated with convulsions at the highest dose tested (100 mg/kg) in female rats only. However, it has been proposed that the application of the PTZ test to assess the pro-convulsive activity of drugs that potentiate or antagonize GABA either directly or indirectly (as in the case with basmisanil, which interacts with the same GABAA receptor) may lead to false-positive conclusions ([Löscher 2009](#)).

Beside the PTZ test, non-clinical study results support the lack of pro-convulsant effect for basmisanil:

- No convulsions and no behavioral abnormalities were observed in the in vivo pharmacology experiments nor in Good Laboratory Practice toxicology experiments including the highest dose groups.
- No effect on audiogenic seizures was observed in DBA/2J mice (a strain that exhibits age-dependent susceptibility to seizure following an auditory stimulus).
- There were no convulsions and no liability for anxiety in GABAA  $\alpha$ 5 knock-out mice.

When basmisanil was used in clinical trials, clinical and EEG monitoring implemented in healthy participants (at doses of up to 1000 mg BID), in adults and children with Down syndrome, and in patients with stroke (at doses of up to 240 mg BID in Phase II studies) did not indicate an increased pro-convulsive liability.

Because epilepsy is present in more than half of the individuals with Dup15q syndrome and previous clinical trials excluded participants with a history of seizures or patients with epilepsy, the risk for basmisanil to exacerbate or trigger de novo seizures in individuals with Dup15q syndrome is not established. Therefore, careful clinical monitoring (including AEs, EEG recording, and determination of seizure status using caregiver reports and diaries) is implemented in this study.

In summary, based on cumulative clinical experience in healthy participants and in adults and children with Down syndrome the potential for basmisanil to trigger de novo seizures or increase the frequency of seizure is considered low and will be carefully assessed in this patient population with a high background incidence of seizures.

Other potential risks described for basmisanil are

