#### **4.1.3 Stopping Rules Criteria**

Dosing will be stopped at any time during the study in a given individual participant if one of the following circumstances occurs:

- A QTc using the Fridericia's correction factor (QTcF) value > 480 msec (when confirmed in repeat measurement within 30 minutes) or a QTcF change from baseline > 60 msec (when confirmed in repeat measurement within 30 minutes) for participants **older than 10 years old**;

OR

- A QTc using Bazett's formula (QTcB) value > 480 msec (when confirmed in repeat measurement within 30 minutes) or a QTcB change from baseline > 60 msec (when confirmed in repeat measurement within 30 minutes) for participants **up to, and including, the age of 10 years** (Bazett's correction is more appropriate in young children, see Section 8.2.6).
- Worsening of seizure frequency or occurrence of de novo seizures, which are considered clinically relevant in the opinion of the Investigator based on the following criteria:
  - persistent over time,
  - OR
  - notably deviate from the expected fluctuations in seizure status based on the participant's medical history,
  - OR
  - cannot be explained by the expected natural course of the disease,
  - OR
  - making the benefit-risk ratio non-favorable for the individual.

Other AEs that may lead to discontinuation of study treatment following evaluation on a case-by-case basis are described in Section 8.3.8. Before permanently discontinuing study treatment, an interruption should be considered, and study treatment may be restarted as detailed in Section 6.6.1. Unless it is determined by the Investigator that the occurrence is not related to the administration of study treatment, study treatment should not be restarted (see Section 7.1).

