### *Remote visits*

*The Day 92, Day 274, early termination, and follow-up visits (Part 1) can be done remotely at the participant's home, if local regulations allow for it. Visits at the participant's home will be conducted by a mobile nurse (MN) professional. The sponsor will select a healthcare company that will be responsible for providing MN services for participating sites. The MN vendor is responsible for ensuring that all MN professionals are licensed, qualified, and in good standing, as per applicable regulations, and that appropriate background checks have been performed.*

*Visits on Day 28 (Part 1) and on Day 457 (Part 2) will be done as a telephone/video call.*

*In addition, during Part 2, mandatory phone calls every 3 months (at minimum) will be done to follow up on AEs, concomitant therapies and to assess suicidality.*

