### **8.2.4 Seizure Status**

The seizure diary (see Section 8.1.3) will be provided to caregivers for completion at home after initial training at the clinic. The *diary* entries are event driven, i.e., have to be completed *retrospectively* after a seizure occurred, and contain information on seizure type, duration, and frequency based on guidance from the International League Against Epilepsy (ILAE; Scheffer et al 2017, Fisher et al 2017). A *list of seizure types is provided for selection by the Investigator based on the "ILAE 2017 Classification of Seizure Types Expanded Version"* (Appendix 7) to support the seizure diary entries.

In addition, the seizure diary asks to confirm accurate entries at regular intervals.

The Investigator will determine the participant's recent seizure status at the timepoints specified in the SoA (*in Part 1 and for the first 6 months in Part 2; see Section 1.3*), based on caregiver report (time since last visit) and review of the information in the seizure diary (see Table 11 for review period for each assessment).

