### **8.3.7      Disease-Related Events and/or Disease-Related Outcomes Not Qualifying as Adverse Events or Serious Adverse Events**

*Seizure activity (i.e., convulsive and non-convulsive seizures) which are in line with the known medical history of the patient should not be reported as AEs unless they meet the seriousness criteria (see [Appendix 2](#)). Only convulsions requiring hospitalization or intubation should be reported as SAEs.*

[figure not shown]

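### Table 1 schedules no clinician review of the seizure diary on treatment before the Day 28 call, 27 days after first dose, and passes over the Day 14 clinic visit

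*Combined protocol and SAP*

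**What the plan says.** Table 1 marks "Seizure status" at Baseline, Days 28, 92, 183, 274 and 365, Follow-up and Early Termination. Screening and Days 1, 2 and 14 are blank. The Day 28 footnote reads "Telephone call only"; Section 8 (Remote visits) is slightly wider: "Visits on Day 28 (Part 1) and on Day 457 (Part 2) will be done as a telephone/video call".

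Section 8.2.4 states: "The Investigator will determine the participant's recent seizure status at the timepoints specified in the SoA". The sources are the caregiver's report and the seizure diary, and Table 11 gives the period covered by each review. Section 4.2.3.1 says that seizure activity may be entered in the seizure status section of the eCRF after the Investigator and caregiver have gone through the diary together.

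Section 4.1.3 lists as an individual reason to stop dosing: "Worsening of seizure frequency or occurrence of de novo seizures, which are considered clinically relevant in the opinion of the Investigator". It applies at any time during the study.

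Section 2.3.1.2 notes that earlier trials excluded people with epilepsy. It judges the risk low from experience elsewhere, but says that "the risk for basmisanil to exacerbate or trigger de novo seizures in individuals with Dup15q syndrome is not established". It therefore promises monitoring made up of adverse events, EEG, and determination of seizure status from caregiver reports and diaries.

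Section 8.3.7 adds that non-serious seizures "which are in line with the known medical history of the patient should not be reported as AEs".

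**The concern.** Every Stage 1 participant has epilepsy, and these children are the first with ongoing seizures to receive the drug. Section 6.5 holds anti-epileptic medication stable for at least the first four weeks of treatment, so a change in seizure frequency is easiest to interpret in that period. Day 14 is a clinic visit with EEG, ECG, laboratory tests and PK sampling, and Section 2.3.1.3 describes it as steady state. A clinician also rates hypotonia there, which is an exploratory endpoint. Yet the one assessment designed to turn diary entries into a clinician's judgement on seizure frequency is not scheduled.

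What is at stake is delay. A rise in frequency that begins in the first two weeks might not be set against the child's history in a planned way until the Day 28 call. The same applies to gaps in diary keeping.

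**Working it through.** The plan states no figure to reproduce. The check is a reading of Table 1, a day count, and a comparison of the surveillance channels.

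**Step 1: read Table 1 against its 12 visit columns.**

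| Row | First marks |
|---|---|
| Seizure status | Baseline, then Day 28 |
| EEG monitoring | Baseline, Days 1, 2 and 14, then Day 183 |
| Caregiver severity rating (CaGI-S) | Baseline, then Days 14 and 28 |
| Clinician severity rating (CGI-S) | Screening, Baseline, then Day 28 |
| Seizure diary | continuous from Screening |

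**Step 2: count the days.** Inputs are the Table 1 visit days, the ± 5 day window on Days 14 and 28, and Baseline between Day −7 and Day −1. There is no Day 0. Days since first dose = visit day − 1. The gap from Baseline on Day −b to visit day d is d + b − 1.

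| First on-treatment review | Days since first dose | With window | Gap from Baseline | With window |
|---|---|---|---|---|
| Day 28 (as planned) | 28 − 1 = 27 | 23 − 1 = 22 to 33 − 1 = 32 | 28 + 1 − 1 = 28 to 28 + 7 − 1 = 34 | 23 to 39 |
| Day 14 (if marked) | 14 − 1 = 13 | 9 − 1 = 8 to 19 − 1 = 18 | 14 to 20 | 9 to 25 |

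The nominal gain is 27 − 13 = 14 days. If Day 14 is held late and Day 28 early, it shrinks to 23 − 19 = 4 days. In the opposite case it is 33 − 9 = 24 days. With two administrations on Day 1 and three daily from Day 2, the administrations before visit day d number 2 + 3 × (d − 2): 80 before Day 28 and 38 before Day 14. This expresses the same interval in another unit and does not measure harm.

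**Step 3: ask what each early channel measures.**

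- *EEG on Days 1, 2 and 14.* Section 8.2.9 makes it a safety measure for seizure activity. It samples the recording period and cannot give seizure frequency over the preceding two weeks.
- *Adverse event enquiry at each contact (Section 8.3.1).* An increase in frequency or intensity of a pre-existing condition is an adverse event (Appendix 2, Section 1; Appendix 3, Section 8). De novo seizures and new seizure types are events of special interest (Section 8.3.6). Non-serious seizures consistent with history are not reported (Section 8.3.7). For a child with known epilepsy, separating these cases means comparing recent counts with history. Section 8.3.2 prefers open, non-leading questions, which is not a structured count.
- *Diary.* It is event-driven and completed by the caregiver. Before Day 28 no clinician review of it is scheduled.
- *Caregiver global ratings at Day 14.* They include a seizures domain (Section 8.1.5.11), but they record an impression rather than a count. They are exploratory efficacy measures and may be completed at home up to 5 days before the visit.

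Of the three safeguards named in Section 2.3.1.2, Day 14 has adverse events and EEG but not determination of seizure status.

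**The case against.** The strongest reply is that the first four weeks are already well watched. EEG findings feed decisions under Section 4.1.3 (Section 8.2.9). A worsening of known seizures is a reportable adverse event and is asked about on Days 2 and 14. The diary prompts caregivers to confirm their entries at regular intervals. Nothing stops a caregiver from calling or an Investigator from opening the diary early. All of this stands, and it rules out several stronger readings that a reader might take from the blank cells:

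- *That seizures go unchecked until Day 28.* They do not, as Step 3 shows.
- *That seizures of a known type are never adverse events.* Section 8.3.7 exempts only non-serious activity in line with history. Serious seizures and a rise in frequency or intensity remain reportable.
- *That the stopping rule cannot operate before Day 28.* It applies at any time on the Investigator's opinion and is not tied to this row.
- *That the opening of Stage 2 rests on a single call.* Section 4.1.2.2 bases it on all available PK, safety and tolerability data from at least 9 participants with four weeks of dosing, including adverse events and the early EEGs.

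It is also fair to say that no missed event or safety effect has been quantified, that the gain can be as small as 4 days within the windows, and that the body of Table 2 and all of Table 11 could not be read in the text available. A further instruction there cannot be excluded. However, the Table 1 row is intact, and Section 8.2.4 describes Table 11 as setting review periods rather than visits.

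**Conclusion.** The point holds in a limited form. Table 1 schedules no clinician review of diary and caregiver report on treatment until 27 days after first dose (22 to 32 with the window), although a steady-state clinic visit falls at 13 days (8 to 18). The other early channels are real, but none is a planned comparison of seizure counts with the child's history. That comparison separates a reportable rise from history-consistent seizures, and it bears directly on the frequency criterion in Section 4.1.3.

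This is a gap in the schedule and a cheap improvement. It is not a contradiction in the plan, and it does not show that participants are unmonitored. The conclusion assumes that Table 1 governs the timing, as Section 8.2.4 says, and that neither Table 2 nor Table 11 adds an earlier review.

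**What to change.** 1. In Table 1, mark Seizure status at Day 14 as a review of the diary with the caregiver, using the existing eCRF section.
2. Align Table 11 so that Day 14 has its own review period and the existing Day 28 review period is left undisturbed. Confirm this against the full table.
3. Include the Day 14 result in the safety data already reviewed by the monitoring and oversight committees before Stage 2 opens.

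The cost is a few minutes at a visit that is already long, plus one more entry per participant. No new visit, equipment or staff is needed, and no dose, stopping criterion or treatment rule changes.
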